Data analysis:	All analyses will be performed with SAS and R. All variables will be summarized descriptively through displays of mean(\pm standard deviations), median, and ranges for continuous variables, and frequency distributions of categorical variables. To address the imbalance of potential confounders between LAMA ICS/LABA groups, we matched treatment groups using propensity scores estimated as by multiple logistic regression analysis based on age, sex, socioeconomic status, Charlson Comorbidity Index, and asthma, and history of COPD exacerbation. Cox proportional hazards regression analyses will be used to estimate hazard ratios (HRs) and 95% confidence intervals (95% CIs) for all outcomes. For (possibly) repeating events (such as exacerbation event) additionally a Poisson regression model will be fitted for the number of events (taking into account the matching). Detailed methodology for summary and statistical analyses of data in this study will be documented in an SAP.		
Milestones:	Start of data collection in 2020 April 15 End of data collection in 2020 Dec 31 Start of data analysis in 2021 Jan 1 End of data analysis in 2021 Dec 31 Final report of study results expected in 2022 Aug		

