8. RESEARCH QUESTION AND OBJECTIVES

In COPD patients, long-term use of ICS is reported to be linked to an increase in the rate of serious pneumonia¹. A study to compare the occurrence of several outcomes after initiation of ICS +LABA therapy with the occurrence after initiation of LAMA therapy in COPD will be conducted. More specifically, the objective is to compare:

- Comparison of pneumonia incidence in COPD patients using LAMA and ICS/LABA
- Comparison of exacerbations frequency and rate in COPD patients using LAMA and ICS/LABA
- Comparison of time to start triple combination therapy (time from initial 'LAMA mono' or ICS+LABA' to 'LAMA+LABA+ICS' combination) in COPD patients using LAMA and ICS/LABA
- Comparison of health care utilization: Medical cost / No. of prescriptions, visits and hospitalizations
- Expected events after long-term use of ICS: osteoporosis, bone fracture, diabetes mellitus, cataracts and recurrence of tuberculosis, Non-tuberculosis Mycobacteria lung disease
- Comparison of all-cause mortality differences in COPD patients using LAMA and ICS/LABA
- Comparison of lung cancer incidence in COPD patients using LAMA and ICS/LABA

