9.3.2.2 Secondary outcomes

Secondary endpoint

- Health care utilization : Medical cost / number of annual visits, prescriptions and hospitalizations (hospitalization mainly due to severe exacerbation of COPD) over one year.
- All-cause mortality
- Recorded incidence of lung cancer (based on ICD-10 code C34.XX)

[REDACTED]

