9.7 DATA ANALYSIS

The study population consists of COPD patients that have received LAMA and ICS/LABA treatment. The study consists of three stages: a) identification and extraction of LAMA-exposed and ICS/LABA-

exposed cohort, b) matching between LAMA-exposed and ICS/LABA-exposed and c) descriptive analysis of cohorts and analysis of outcomes.

Detailed methodology for summary and statistical analyses of data generated in this study will be documented in an SAP. The SAP may modify the plans outlined in the protocol; any major modifications of primary endpoint definitions or their analyses would be reflected in a protocol amendment.

For the purpose of this study, analyses will be conducted using SAS statistical software and R. To address the imbalance of potential confounders between LAMA ICS/LABA groups, we matched treatment groups using propensity scores estimated as by multiple logistic regression analysis *based on* as age, sex, socioeconomics status, *Charlson Comorbidity Index*, and asthma, history of COPD exacerbation. Demographics and clinical characteristics will be tabulated. Frequencies and percentages will be presented for categorical variables. For continuous variables, means, standard deviations, and ranges, or medians and inter-quartile ranges, will be reported as appropriate. We used a standardised difference to compare baseline characteristics between COPD patients who were treated with LAMA and those treated with ICS/LABA. The matched Cox proportional hazards regression analyses will be used to estimate hazard ratios (HRs) HRs and 95% confidence intervals (95% CIs) for all outcomes. For (possibly) repeating events (such as *exacerbation event*) *additionally* a Poisson regression model will be fitted for the number of events (taking into account the matching). The cox and Poisson models will be adjusted for unbalanced PS-variables at baseline. Mortality was estimated by the Kaplan-Meier method, and results were compared between groups using the log-rank test.

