9.7.2 Main analysis

For the primary effectiveness outcomes incidence rates (events per 1,000patients-years) with corresponding 95% confidence intervals (CI) will be calculated. This will be evaluated by a matched Cox proportional hazards regression model for counting processes, which allow the follow-up time to be divided into several periods and therefore control for baseline and time-dependent covariates, using the full observational period of available data, i.e. up to 11 years of follow up. The Cox proportional hazards regression will take into account the fact that individual matching (1:1) will be performed by considering the exposed patient and his/her matched controls as one stratum and including this as a stratum in the Cox proportional hazards model. Additional variables will be included in the model if available. The cumulative incidence plots will be accompanied by number of patients at risk at different time points during follow-up. For (possibly) repeating events (such as exacerbation event) additionally a Poisson regression model will be fitted for the number of events (taking into account the matching). Time in the study will be included as an offset variable in the model. The cox and Poisson models will be adjusted for unbalanced PS-variables at baseline.

The outcome will be analyzed separately for each:

- 1) Primary outcome
 - Comparison of pneumonia incidence in COPD patients using LAMA and ICS/LABA
 - Comparison of exacerbations frequency and rate in COPD patients using LAMA and ICS/LABA : moderate or severe exacerbation

Proprietary confidential information © 2022 Boehringer Ingelheim International GmbH or one or more of its affiliated companies

[figure not shown]
- Comparison of time to start triple combination therapy (time from initial 'LAMA mono' or ICS+LABA' to 'LAMA+LABA+ICS' combination) in COPD patients using LAMA and ICS/LABA

2) Secondary outcome

- Comparison of all-cause mortality differences in COPD patients using LAMA and ICS/LABA
- Comparison of lung cancer incidence in COPD patients using LAMA and ICS/LABA
- Comparison of health care utilization: Medical cost / No. of prescriptions, visits and hospitalizations (hospitalization mainly due to severe exacerbation of COPD)

Health care utilization

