Health care utilization outcomes will be analyzed separately in each treatment group. Analyses will be conducted for 1)total health care expenditure 2)COPD-related utilization and cost for all of the medical resource utilization and costs during the follow-up period. For outpatient services, analyses were confined to visits with the ICD-10 code of COPD (J43.x–J44.x, except J430) with the prescription of COPD-related medication. For inpatient services, analyses were confined to admission with ICD-10 code of COPD or COPD-related disease (pneumonia: J12.x–J17.x, pulmonary thromboembolism: I26, I26.0, and I26.9; dyspnea: R06.0; or acute respiratory distress syndrome: J80) with the prescription of COPD-related medication. Medical costs per person per year will be reported overall and separately based on type of service: inpatient healthcare visits, outpatient healthcare visits, and pharmacy dispensations. This involves calculating the average cost among members who are alive in the beginning of a month.

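### Health care utilisation is a between-treatment comparison, but the plan names no workable between-group method for medical cost and does not say whether its Poisson model applies to the utilisation counts

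*Combined protocol and SAP*

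**What the plan says.** Section 8 gives the objective as "Comparison of health care utilization: Medical cost / No. of prescriptions, visits and hospitalizations". Section 9.3.2.2 makes it a secondary endpoint: "Medical cost / number of annual visits, prescriptions and hospitalizations", assessed over one year. Section 9.7.2 repeats it in the list of secondary outcomes: "Comparison of health care utilization: Medical cost / No. of prescriptions, visits and hospitalizations (hospitalization mainly due to severe exacerbation of COPD".

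The dedicated paragraph at the end of Section 9.7.2 begins "Health care utilization outcomes will be analyzed separately in each treatment group". It goes on to define total and COPD-related use and cost over follow-up, yearly cost per patient by type of service, and a mean taken over those still living when each month opens.

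Two general between-group models appear elsewhere:

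- **Cox.** Section 9.7 promises "hazard ratios (HRs) HRs and 95% confidence intervals (95% CIs) for all outcomes" from the matched Cox model. The abstract says the same: "hazard ratios (HRs) and 95% confidence intervals (95% CIs) for all outcomes".
- **Poisson.** For outcomes that can recur, with exacerbation as the example, Section 9.7.2 adds that "a Poisson regression model will be fitted for the number of events (taking into account the matching"), and "Time in the study will be included as an offset variable in the model".

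Both models are to be adjusted for propensity-score variables that remain unbalanced.

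**The concern.** The objective asks how the two treatments differ. The rule written for this endpoint describes each arm on its own and names no difference, ratio, test, interval or use of the matched pairs. The general rule that claims to cover every outcome produces a hazard ratio, which is not a measure of annual cost.

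At stake is the cost part of a stated secondary objective. The report could present two average costs with no estimate of the difference, no statement of its uncertainty and no adjustment for imbalance left after matching. For visits, prescriptions and hospitalisations, two analysts could follow the same text and do different things: one would tabulate by arm, the other would fit the Poisson model.

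**Working it through.** The plan states no figure for this comparison, so there is none to reproduce. The main check sets each utilisation component against each rule in the plan.

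| Component | Utilisation paragraph, 9.7.2 | Cox, abstract and 9.7 | Poisson, 9.7.2 |
|---|---|---|---|
| Medical cost | Arm-wise average, no contrast | Not applicable: a cost is an amount, not a time to an event | Not applicable: written for numbers of events |
| Visits, prescriptions, hospitalisations | Arm-wise, no contrast | Usable only if recast as event times | Could apply: recurring counts with a time offset; not invoked |

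Cost therefore has no between-group method that fits it. The counts have one that could fit, beside a specific rule that says something else.

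**Matching and adjustment.** Section 9.7 places matching before the analysis of outcomes, so the arm-wise averages would presumably come from matched arms. Section 9.7.1.1 says that variables with a standardised difference above 0.1 will be adjusted for. Cost has no between-group model in which to do that.

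**Window.** Section 9.3.2.2 refers to one year, while the utilisation paragraph refers to follow-up, which Section 9.7.2 puts at up to 11 years. The contrast cannot be defined until one is chosen.

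**Could the planned size support a cost contrast?** This is illustration only. The input from Section 9.5 is n = 5,000 per arm, an expected minimum and not a power calculation. The coefficient of variation (CV) of cost is not given, so I assume 1, 2 and 3. Pairing is ignored.

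Half-width of the 95% interval for the difference, as a share of the mean = 1.96 × CV × √(2/5,000) = 1.96 × CV × 0.02.

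- CV 1: 1.96 × 0.02 = 3.9%
- CV 2: 1.96 × 0.04 = 7.8%
- CV 3: 1.96 × 0.06 = 11.8%

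**Counts.** The factor by which a rate ratio is multiplied or divided to reach its 95% limits is exp(1.96 × √(2φ/(5,000 × r))), for an assumed rate r per person-year, one year of follow-up and overdispersion φ.

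- r = 0.2: 1.092 at φ = 1 and 1.192 at φ = 4
- r = 1: 1.040 and 1.082
- r = 5: 1.018 and 1.036

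Overdispersion of 4 doubles the standard error on the log scale, so the variance method for the counts should be stated.

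**The case against.** The strongest reply is that the plan is not confined to Cox. The Poisson model allows for the matching, carries a time offset and is adjusted for residual imbalance, and exacerbation is only an example of what it covers. Three of the four utilisation components can therefore be read as having a between-group rate ratio. This stands. A reader might infer that the plan offers no valid between-group estimate for any utilisation outcome, or that Cox is its only comparative method; the text on recurring events does not support either inference. The Cox model in Section 9.7.2 is also in counting-process form, which can handle recurrent events, so a hazard ratio is not meaningless for hospitalisations or visits.

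A second reply is that an arm-wise analysis may only mean tabulating costs by arm before the comparison listed just above it. That is possible, but no comparison step for cost follows.

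A third is that detail is left to a SAP. No separate SAP text is in the document, and blacked-out text cannot be checked. Deferral softens the gap. It does not remove it, because the protocol already states a rule that falls short of its objective, and Section 9.7 promises an amendment only for major changes to primary endpoints or their analyses.

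Finally, a reader might go further and claim that real cost differences would be missed by judging overlap of separate intervals. At CV 2, separate intervals part only above 2 × 1.96 × 2/√5,000 = 11.1%, against 7.8% for a direct contrast. The plan promises no arm-wise intervals for cost, so that loss cannot be attributed to it.

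**Conclusion.** The point holds in full for medical cost: followed as written, the readable plan gives no valid between-group estimate or interval for that part of a secondary endpoint. For the counts it is a lack of clarity: a suitable model exists, but the specific rule does not call on it. It would be too strong to say that the arm-wise figures ignore the matching, since the order of steps in Section 9.7 suggests otherwise.

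The half-widths of 3.9% to 11.8% show only that a contrast is feasible. They rest on assumed CVs of 1 to 3, 5,000 per arm and independent arms; a larger cohort would narrow them. The primary outcomes are not affected. The matter should be settled before the analysis.

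**What to change.** Replace the arm-by-arm sentence in Section 9.7.2 with a between-group analysis in the matched cohort, and carry it into the SAP.

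- **Cost:** report the ratio and difference of means with 95% intervals, for example from a log-link generalised linear model with pair-clustered robust or pair-bootstrap variance, adjusted for propensity-score variables with a standardised difference above 0.1. State how death and censoring are handled. Other models would serve; naming one matters more than which.
- **Counts:** state that the Section 9.7.2 count model with its time offset applies to visits, prescriptions and hospitalisations, with pair-robust variance, or negative binomial if overdispersed.
- **Hazard ratios:** in the abstract and Section 9.7, limit the promise to time-to-event outcomes, including recurrent events in counting-process form if intended.
- **Window:** reconcile the one-year window in Section 9.3.2.2 with the follow-up window in Section 9.7.2.

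Arm-wise tables can stay as description. The cost is a few sentences and a few extra models on data already to be extracted.

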9.3.2 Outcomes

9.3.2.1 Primary outcomes

Primary endpoint

- Recorded pneumonia based on 1)ICD-10 code (J12.x-J18.x, J69.0, J84.9, B96.0, J85.1) AND 2) CPT code of chest x-ray(71045-71048) or chest CT(71250,71260,71270,G0297) AND 3) prescription of antibiotics for pneumonia in Korean Guideline) incidence rate per year
- Frequency rate of COPD exacerbation per year
 - Moderate exacerbation: recorded as when COPD patients visited outpatient clinics with an ICD-10 code of COPD and systemic steroid medication and/or antibiotics were prescribed (within the first year after initial prescription of inhalers)
 - Severe exacerbation: when COPD patients visited the emergency room or were admitted to hospital with an ICD-10 code of COPD(*due to COPD worsening*) and were prescribed systemic steroid medication and/or antibiotics (within the first year after initial prescription of inhalers)
- Time to start triple combination therapy ICS/LABA/LAMA)
 - Time to add LAMA in patients with using ICS/LABA or, time to add ICS/LABA in patients with using LAMA before.

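### COPD-related inpatient utilisation counts pneumonia as J12–J17 while the primary endpoint counts J12–J18, so some J18 admissions drop out of that one analysis

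*Combined protocol and SAP*

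**What the plan says.** Section 9.3.2.1 defines the first primary endpoint as "Recorded pneumonia based on 1)ICD-10 code (J12.x-J18.x, J69.0, J84.9, B96.0, J85.1", and also requires chest imaging and an antibiotic for pneumonia.

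Section 9.3.2.2 names a secondary endpoint: "Health care utilization : Medical cost / number of annual visits, prescriptions and hospitalizations". Section 9.7.2 splits it in two: "Analyses will be conducted for 1)total health care expenditure 2)COPD-related utilization and cost". For the COPD-related part:

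- outpatient care is limited to "visits with the ICD-10 code of COPD (J43.x–J44.x, except J430) with the prescription of COPD-related medication";
- inpatient care is wider: "For inpatient services, analyses were confined to admission with ICD-10 code of COPD or COPD-related disease". The list of COPD-related diseases opens "pneumonia: J12.x–J17.x, pulmonary thromboembolism" (the latter coded I26, I26.0 and I26.9) and ends with R06.0 and J80. A prescription of COPD-related medication is required here too.

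Sections 9.3 and 9.7 leave detailed definitions to an SAP. Nothing in the readable text explains why the inpatient range ends at J17, and nothing adds J18 back.

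**The concern.** The protocol uses two code lists for one disease. Because the inpatient rule joins the COPD code and the disease list with OR, the pneumonia list matters only for admissions that have no COPD code. The rule sets out to treat such pneumonia admissions as COPD-related, and then omits a category that the same protocol calls pneumonia.

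The omission need not fall evenly on the arms. Section 8 gives the motivation for the study: "long-term use of ICS is reported to be linked to an increase in the rate of serious pneumonia". If that holds here, the missing admissions are more numerous on ICS/LABA, in a component where a difference between the arms is expected. The abstract also plans a sub-analysis of pneumonia-related hospitalisation. The report could then show pneumonia admissions in one table that are absent from its COPD-related inpatient table, with no stated reason.

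**Working it through.** The plan gives no figure to reproduce. The check compares the two lists and then follows the consequence.

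**Step 1: set the lists side by side.**

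| Code | Primary pneumonia endpoint (9.3.2.1) | COPD-related inpatient list (9.7.2) |
|---|---|---|
| J12.x–J17.x | yes | yes |
| J18.x | yes | no |
| J69.0, J84.9, B96.0, J85.1 | yes | no |
| I26, R06.0, J80 | no | yes |
| J43.x–J44.x except J430 | no | yes (as COPD) |

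**Step 2: which admissions are lost.** A J18 admission is lost through the code list only if all of these hold:

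- it has no COPD code;
- it has no other listed code (J12–J17, I26, R06.0, J80);
- COPD-related medication was prescribed. Without that prescription, it would be excluded whatever the list says.

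If it also meets the imaging and antibiotic conditions, it can be a primary pneumonia event.

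**Step 3: direction.** Let T be the rate of COPD-related admissions in an arm with J18 included, and L the rate of lost admissions. The analysis as written sees T − L, so the difference it sees is

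(T_ICS/LABA − T_LAMA) − (L_ICS/LABA − L_LAMA).

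If pneumonia is more frequent on ICS/LABA and the same fraction is lost in both arms, L is larger on ICS/LABA. The difference is pushed down, and an excess on ICS/LABA looks smaller than it is. The same holds for cost if a lost admission costs about the same in both arms.

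**Step 4: what can be said about size.** The documents give neither the share of pneumonia admissions coded J18 nor the share of those with no other qualifying code. By assumption only, take pneumonia admissions that meet the medication condition. Suppose 20% to 80% carry J18, and 10% to 50% of those have no COPD or other listed code:

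- low: 0.20 × 0.10 = 0.02, or 2% lost;
- high: 0.80 × 0.50 = 0.40, or 40% lost.

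With assumed pneumonia admission rates of 3.0 (LAMA) and 4.5 (ICS/LABA) per 100 person-years, the true difference is 4.5 − 3.0 = 1.5. It would appear as 1.5 × 0.98 = 1.47 at the low end and 1.5 × 0.60 = 0.90 at the high end. The pneumonia rate ratio stays at 4.5 / 3.0 = 1.5, because equal proportional loss cancels.

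These figures describe pneumonia admissions alone. The outcome is all COPD-related admissions and cost, and the documents do not give the pneumonia share of either.

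**The case against.** The strongest reply is that the lists serve different purposes. One defines a disease outcome, and the other attributes admissions to COPD. No passage requires every primary pneumonia event to count as COPD-related, and sections 9.3.2.2 and 9.7.2 describe the hospitalisation component as driven mainly by severe exacerbation. That much stands: different lists could be deliberate. But section 9.7.2 does include pneumonia without a COPD code, and gives no reason why J12–J17 qualifies and J18 does not.

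Several stronger readings are tempting, and the documents do not support them:

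- **The whole cost comparison is biased.** Section 9.7.2 also plans total health care expenditure, which on its natural reading keeps these admissions.
- **Copying the primary list would make every primary pneumonia admission count.** It would not, because the medication condition remains. It would also bring in J69.0, J84.9, B96.0 and J85.1, whose place in COPD-related cost needs its own justification.
- **The loss is known to be large.** Its size rests wholly on assumed shares, and the low end of the illustration is 2%. Under equal proportional loss the pneumonia rate ratio does not change at all.

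It is also fair to say that this is a secondary endpoint and that the SAP may still settle the definition. That makes the correction easy, but the rule as it now stands does leave the admissions out.

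**Conclusion.** The mismatch is certain, since both code ranges stand in the text. As written, section 9.7.2 leaves out of the COPD-related inpatient analysis any J18 admission that has COPD-related medication but no COPD code and no other listed code, although it can be a primary pneumonia event.

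The direction is conditional. It assumes that pneumonia is more frequent on ICS/LABA and that coding habits are similar in the two arms. The absolute ICS/LABA minus LAMA difference in COPD-related inpatient utilisation and cost is then too low. The size cannot be computed from the documents, and no figure should be quoted as an estimate of it. The point is limited to one of two analyses within one secondary endpoint, but it is worth correcting before analysis because the rule is wrong as written and simple to repair.

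**What to change.** In section 9.7.2, or in the SAP before analysis:

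1. Change the inpatient pneumonia range to J12.x–J18.x.
2. Keep the COPD-related medication condition.
3. For J69.0, J84.9, B96.0 and J85.1, either add them or state why they are not COPD-related.
4. Report the J12.x–J17.x list as a sensitivity analysis, which also shows how much the choice matters.

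The cost is one line in the code list, a sentence of justification for the four remaining codes, and one extra run. Diagnosis codes are already among the variables to be extracted (section 9.6 and Appendix Table 1), so no new data are needed.
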